### 6.6.3 ECG Assessment

Safety ECGs will be performed as outlined in Appendix 1, schedules of procedures and events. Post-screening ECGs will be compared with screening ECG.

The PI or sub-investigator (physician) will be responsible for review and interpretation of safety ECG on site and determining if the ECG is normal, abnormal “not clinically significant” or abnormal “clinically significant”. Findings will be documented in the CRF. This information will be used in the continuous safety review during the conduct of the trial. The ECGs will also be read and interpreted by the central ECG laboratory.

[REDACTED]

[REDACTED]

[REDACTED]

[REDACTED]

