#### 9.8.6 Safety ECG (12-lead ECG) [REDACTED]

Individual safety ECG (12-lead) values will be listed by treatment and visit, and summarized using descriptive statistics. Intervals to be provided for each ECG are: RR, PR, QRS, QT, QTc, QTcB, and QTcF. Post-screening ECGs will be compared with the baseline ECG. Any clinically significant change from baseline may be recorded as an AE if deemed appropriate by the PI or sponsor.

[REDACTED]

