## 9. SAFETY ANALYSIS

The safety of etrasimod will be monitored throughout the study with safety endpoints being as follows:

- Treatment-emergent adverse events (TEAEs) up to 30 days following discontinuation of the study drug
- Treatment-emergent serious adverse events (SAEs) up to 30 days following discontinuation of the study drug

Additional safety assessments will include:

- Physical & neurological examinations including ophthalmoscopy (and optical coherence tomography [OCT], where available)
- Progressive multifocal leukoencephalopathy (PML) checklist
- Clinical laboratory tests to include hematology, serum chemistry, coagulation, and urinalysis
- Vital sign measurements
- Pulmonary Function Tests (PFTs)
- ECGs
- AE reporting

For analyses based on laboratory measurements, vital signs and ECGs, summary tabulations (n, mean, SD, median, minimum and maximum for actual and change [or percent change] from baseline) will be presented. For analyses based on AEs, frequency and percentage will be presented. The analyses for all safety outcomes (categorical or continuous measures) will use the Safety population.

For analysis based on laboratory measurements, at least 1 laboratory test post-enrollment measurement in the extension study is required for inclusion in the Safety population. When assessing change from baseline, a baseline measurement is also required. Baseline for the safety analysis is defined as the last pre-enrollment measurement (i.e. APD334-005 Day 1 pre-dose). No missing data will be imputed for the safety analysis.

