## **9.2. Clinical Laboratory Evaluations**

Clinical laboratory evaluations (i.e. hematology, serum chemistry, coagulation and urinalysis) will be performed by a central laboratory. All summaries will be based on the units provided by the central laboratory, no conversion will be performed.

Summary tabulations (i.e. n, mean, SD, median, minimum and maximum) for the observed values and changes from baseline will be presented for clinical laboratory evaluations with numeric values for patients in the Safety population. Observed results at each visit and changes from baselines (APD334-003 baseline and APD334-005 baseline) to each scheduled post-baseline visit will be presented.

All relevant clinical laboratory tests will be classified as Low, Normal, and High according to the normal ranges. This categorical data will be summarized in shift tables comparing the results at last scheduled post-baseline visit with those at the baseline visit. Baseline for APD334-003 study is defined as last measurement before first dose of study medication in APD334-003 study, and baseline for APD334-005 study is defined as last pre-enrollment measurement (APD334-005 Day 1 pre-dose).

If any laboratory value falls above or below the upper or lower level of quantification, the value of the upper or lower level of quantification will be taken (e.g.  $<0.2$  will become 0.2) for summaries but left as recorded in the listing.

All individual lab values will be listed by visit.

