### **9.3. Vital Sign Measurements**

Supine (laying face upward) blood pressure, heart rate/pulse, temperature, and respiratory rate will be measured after the patient has been resting for 5 minutes. Vitals signs will be measured prior to any blood draw that occurs at the same time point. Vital signs will be measured according to the time points in the schedules of procedures and visits (Section 14.1).

Summary tabulations (i.e. n, mean, SD, median, minimum and maximum) for the observed values and changes from baseline will be presented for vital sign data for patients in the Safety population. Changes from baselines (APD334-003 baseline and APD334-005 baseline) to each scheduled post-baseline time point and visit will be presented. Baseline for APD334-003 study is defined as last measurement before first dose of study medication in APD334-003 study, and baseline for APD334-005 study is defined as last pre-enrollment measurement (APD334-005 Day 1 pre-dose).

All vital sign data by patient will be presented in a listing.

[figure not shown]

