### **9.5. Safety ECG (12-lead)**

Safety ECGs will be recorded from an ECG machine (12-lead). All safety ECGs will be obtained as single tracings, with the exception of the pre-treatment ECG obtained on Day 1, which is a triplicate recording.

All patients will have a standard 12-lead ECG performed during the study as clinically indicated. Intervals to be provided for each ECG are: RR, PR, QRS, QT, QT interval corrected for heart rate (QTc), QTc corrected by Bazett's (QTcB), and QTc corrected by Fridericia's (QTcF).

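### In the visible text, ECG change has one baseline, APD334-005 Day 1, which follows 12 weeks of drug for patients from the active arms; laboratory tests and vital signs also get the APD334-003 baseline

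*SAP*

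**What the plan says.** SAP 9 sets the general rule for safety summaries and names ECGs in it: "For analyses based on laboratory measurements, vital signs and ECGs, summary tabulations (n, mean, SD, median, minimum and maximum for actual and change" from baseline. The same section then fixes the reference point: "Baseline for the safety analysis is defined as the last pre-enrollment measurement (i.e. APD334-005 Day 1 pre-dose".

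Two of the measures under that rule are given a second reference later. For laboratory tests, SAP 9.2 states: "Observed results at each visit and changes from baselines (APD334-003 baseline and APD334-005 baseline) to each scheduled post-baseline visit will be presented". For vital signs, SAP 9.3 states: "Changes from baselines (APD334-003 baseline and APD334-005 baseline) to each scheduled post-baseline time point and visit will be presented". Both sections define the APD334-003 baseline as the last value before the first dose in that study.

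The visible text of SAP 9.5 covers how ECGs are recorded and which intervals are reported ("Intervals to be provided for each ECG are: RR, PR, QRS, QT, QT interval corrected for heart rate (QTc", followed by the Bazett and Fridericia corrections). It names no baseline and describes no summary table.

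The protocol uses two terms for the ECG comparator. Section 6.6.3 says "Post-screening ECGs will be compared with screening ECG"; section 9.8.6 says "Post-screening ECGs will be compared with the baseline ECG".

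**The concern.** The primary objective is long-term safety. For a patient who took 1 mg or 2 mg in the 12-week parent study, the Day 1 pre-dose ECG is taken after that exposure. The extension drug is dispensed at the parent study's Week 12 visit, and the visible text describes no washout. Change from Day 1 then answers a narrower question: what happened after Week 12. For a patient from the 1 mg arm it shows the step from 1 mg to 2 mg plus any later drift.

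Patients from the placebo arm have a Day 1 ECG free of study drug, but their drug exposure under the current design is at most 34 weeks. Under the Day 1 rule, therefore, no column shows ECG change from a drug-free baseline over the full 46 weeks. The SAP treats that longer span as relevant elsewhere: section 7.2.2 summarises exposure from the start of APD334-003, and section 8.3 measures response against the APD334-003 baseline.

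The overall 2 mg column in SAP 4 combines patients from all three parent-study arms, so its mean ECG change mixes two kinds of baseline. A reader could take a small pooled change as evidence of little ECG effect when part of the effect had already been subtracted.

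**Working it through.** **Baselines side by side (visible text)**

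| Measure | Section | APD334-005 Day 1 baseline | APD334-003 baseline |
|---|---|---|---|
| Laboratory tests | SAP 9.2 | yes | yes |
| Vital signs, including heart rate | SAP 9.3 | yes | yes |
| ECG intervals | SAP 9, 9.5 | yes, by the general rule | not stated |

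**Direction of the effect.** The plan states no ECG figure, so there is nothing to reproduce. The following is illustrative, and all three inputs are assumptions:

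- D: true change in an interval from a drug-free baseline, taken as equal in all patients
- f: share of the pooled 2 mg column that came from the 1 mg and 2 mg arms
- g: share of D already present at Week 12 in those patients

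Mean change from Day 1:

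- prior-placebo column: D
- prior-active columns: (1 − g) × D
- pooled 2 mg column: (1 − f) × D + f × (1 − g) × D = (1 − f × g) × D

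Example: f = 2/3, g = 0.5 gives 1 − 0.33 = 0.67, so 0.67 D.

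| | g = 0 | g = 0.5 | g = 1 |
|---|---|---|---|
| Prior-active columns | 1.00 D | 0.50 D | 0 |
| Pooled, f = 0.5 | 1.00 D | 0.75 D | 0.50 D |
| Pooled, f = 2/3 | 1.00 D | 0.67 D | 0.33 D |
| Pooled, f = 0.8 | 1.00 D | 0.60 D | 0.20 D |

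With the APD334-003 baseline for everyone, each of these columns shows 1.00 D under the same assumptions. Attenuation needs only g > 0; if no ECG effect is present by Week 12, the Day 1 baseline loses nothing. Using one g for both active arms is a simplification, since patients from the 1 mg arm change dose.

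**Protocol comparator.** Section 6.6.3 is a procedures section and 9.8.6 an analysis section. The visible protocol describes no separate APD334-005 screening visit, but the schedule in Appendix 1 is not available and section 7.2.1 is partly redacted. The screening ECG could therefore mean the parent study's screening ECG, and the text does not settle it.

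**The case against.** The strongest reply is redaction. The contents entry for SAP 9.5 carries a redaction mark, and the parallel Protocol 9.8.6 is redacted in its heading and after its visible text. A two-baseline sentence for ECG may have been removed, and removed text is not missing text. The Day 1 sentence in SAP 9 also covers laboratory tests and vital signs, which still receive a second baseline, so it does not exclude one for ECG. SAP 9.6 likewise uses the plural for lymphocyte counts. This stands: a reader might infer that the plan measures ECG change only from Day 1, and the documents support that for the visible text alone.

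A reader might also infer that the long-term ECG effect is hidden. That is too strong. Actual ECG values are tabulated beside change, SAP 4 splits summaries by previous treatment, the prior-placebo column starts free of study drug, and any new change after Week 12 remains visible in every column. Heart rate is not lost either, because SAP 9.3 reports it from both baselines.

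It is fair to add that the primary endpoints are adverse events and serious adverse events, that ECGs are an additional safety assessment, and that no hypothesis is tested. That limits the weight of the point. It does not explain why ECG intervals should visibly have one baseline when the other two measures named in the same sentence have two.

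**Conclusion.** The point holds for the visible text. Followed as written, the plan removes from ECG change any PR, QRS or QTc effect already present at Week 12 in patients from the active arms, and it mixes drug-free and on-drug baselines in the pooled 2 mg column.

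The size cannot be computed. It is tempting to say that the pooled column would show 33% to 50% of the true change, but that range needs an assumed active-arm share of 2/3 to 0.5 and the whole effect present by Week 12. The documents support neither assumption, and with no effect present by Week 12 there is no loss. The conclusion rests on there being some ECG effect at Week 12, on no washout before Day 1, and on no redacted second-baseline rule in SAP 9.5.

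The difference between Protocol 6.6.3 and 9.8.6 is a minor matter of wording to reconcile. The documents do not show that sites and analysts would in fact use different ECGs.

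**What to change.** - **SAP 9.5:** unless redacted text already says so, state that ECG intervals are summarised as change from both the APD334-003 baseline (last ECG before the first APD334-003 dose) and the APD334-005 baseline, as SAP 9.2 and 9.3 do for their measures.
- **SAP 9:** align the single-baseline sentence with the two-baseline sections, so that the general rule and the specific ones agree.
- **Protocol 6.6.3 and 9.8.6:** name one ECG comparator, and say which study's ECG it is.

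The cost is SAP and protocol wording plus one extra set of table columns. No new procedure is needed, assuming that pre-dose APD334-003 ECGs exist and can be brought into the extension database.

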### 9.1. Adverse Events

A TEAE is defined as an AE that meets any of the following conditions:

- begins on or after the first dose of study drug in APD334-005 study

- begins before the first dose of study drug in APD334-005 study and worsens in severity on or after the first dose of study drug in APD334-005 study
- occurs in APD334-003 study and is ongoing in APD334-005 study
- occurs in APD334-003 study and end date is in APD334-005 study
- is completely missing an onset date and end date
- is completely missing an onset date and the end date is on or after the first dose of study drug in APD334-005 study

For the purpose of inclusion in TEAE tables, incomplete AE onset and end dates will be imputed as follows:

Missing onset dates (where UK and UKN indicate unknown or missing day and month respectively):

- UK-MMM-YYYY: If the month and year are different from the month and year of the first dose of study drug, assume 01-MMM-YYYY. If the month and year are the same as the first dose of study drug month and year, and the end date (after any imputation) is on or after the first dose of study drug, then assume the date of the first dose of study drug. If the month and year are the same as the first dose of study drug month, and year and the end date (after any imputation) is prior to the first dose of study drug, then assume the end date for the onset date
- DD-UKN-YYYY/UK-UKN-YYYY: If the year is different from the year of first dose of study drug, assume 01-JAN-YYYY of the collected year. If the year is the same as the first dose of study drug year, and the end date (after any imputation) is on or after the first dose of study drug, then assume the date of the first dose of study drug. If the year is the same as the first dose of study drug, and the end date (after any imputation) is prior to the first dose of study drug, then assume the end date for the onset date

Missing end dates (where UK and UKN indicate unknown or missing day and month respectively):

- UK-MMM-YYYY: Assume the last day of the month
- DD-UKN-YYYY/UK-UKN-YYYY: Assume 31-DEC-YYYY

All AEs will be classified by System Organ Class (SOC) and Preferred Term (PT) according to the Medical Dictionary for Regulatory Activities (MedDRA, version 20.1).

Patients with at least one TEAE will be summarized for the following:

- Overall summary of TEAEs
- Summary of TEAEs by SOC and PT
- Summary of TEAEs by Relationship to Study Drug
- Summary of TEAEs by Severity
- Serious TEAEs by SOC and PT
- TEAEs that leading to permanent discontinuation of study drug by SOC and PT
- TEAEs with severity grade  $\geq 3$  by SOC and PT

Patients will be monitored from Informed Consent Form (ICF) signature to 30 days after the last dose of study drug for adverse reactions to the study drug and/or procedures.

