#### 3.2. Study Endpoints

##### 3.2.1. Primary Endpoint

The primary endpoint for the study is long-term safety. The safety of etrasimod will be monitored throughout the study with safety endpoints being as follows:

- Treatment-emergent adverse events (TEAEs) up to 30 days following discontinuation of the study drug

[figure not shown]
- Treatment-emergent serious adverse events (SAEs) up to 30 days following discontinuation of the study drug

[figure not shown]

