## 4. GENERAL STATISTICAL CONSIDERATIONS

Continuous data will be summarized using descriptive statistics (i.e., n, mean, median, standard deviation (SD), 90% confidence interval (CI) for change or percent change from baseline, minimum and maximum). For the summary statistics of all numerical variables unless otherwise specified, minimum and maximum will be displayed to the same level of precision as reported. Mean, median and 90% CIs will be displayed to one level of precision greater than the data collected. Standard deviation will be displayed to two levels of precision greater than the data collected.

For proportion-based measures, n, frequencies, proportion and its 90% CI will be produced. The denominator for all percentages will be the number of patients within the treatment group for the analysis set of interest, unless otherwise stated. Percentages will be presented to 1 decimal place. When count data are presented, the percentage will be suppressed when the count is zero in order to draw attention to the non-zero counts. A row denoted “Missing” will be included in count tabulations where specified on the shells to account for dropouts and missing values.

There is no formal between group inferential comparisons for study endpoints due to lack of control group. Summary statistics will be provided for the primary safety endpoint, secondary efficacy endpoints, exploratory efficacy endpoints, and additional safety measures. All analysis summaries will be presented as follows:

Previously Treated in APD334-003 (APD334-005 treatment: 2 mg etrasimod)				APD334-005 treatment:	APD334-005 treatment:
Placebo	1 mg etrasimod	2 mg etrasimod	1 mg & 2 mg etrasimod	2 mg etrasimod	Placebo

[figure not shown]
[figure not shown]
Listings will include a subtitle to indicate both treatments, i.e. treatment received in APD334-003 study and treatment received in APD334-005 study.

[figure not shown]
[figure not shown]
[figure not shown]
If endoscopy was performed prior to Week 46, then last observation carried forward (LOCF) imputation method will be used for the endoscopy subscore. Any endoscopy performed during the APD334-005 extension study (after Week 12 visit) will be used for LOCF imputation.

All data summaries and statistical analyses will be performed using the SAS software version 9.3 or higher (SAS Institute, Cary, NC).

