### **9.1.2. Treatment Emergent Adverse Events Summary by SOC and PT**

Summaries of the total number of TEAEs and the number and percentage of patients with at least one TEAE will be provided. TEAEs will be presented by SOC and PT. At each level of patient summarization, a patient is counted once if the patient reported one or more events. Percentages will be calculated out of the number of patients in the Safety population.

The summary of TEAEs will be presented in descending order from the SOC with the highest total incidence (that is, summed across all treatment groups) to the SOC with the lowest total incidence. If the total incidence for any two or more SOCs is equal, the SOCs will be presented in alphabetical order. Within each SOC, the PTs will be presented in alphabetical order.

All TEAEs will be presented in a listing.

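### SAP 9.1 counts unworsened APD334-003 events as treatment-emergent in APD334-005, so the primary-endpoint tables mix new and carried-over events

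*SAP*

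**What the plan says.** SAP 3.2.1 states: "The primary endpoint for the study is long-term safety". It is measured by TEAEs and treatment-emergent serious events up to 30 days after study drug is stopped.

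SAP 9.1 then defines the term: "A TEAE is defined as an AE that meets any of the following conditions". The six conditions are, in order:

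1. onset on or after the first APD334-005 dose;
2. "begins before the first dose of study drug in APD334-005 study and worsens in severity on or after the first dose of study drug" (the APD334-005 dose);
3. "occurs in APD334-003 study and is ongoing in APD334-005 study";
4. "occurs in APD334-003 study and end date is in APD334-005 study";
5. onset and end dates both wholly missing;
6. onset date wholly missing, with an end date on or after the first APD334-005 dose.

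The overall, SOC/PT, relationship, severity, serious, discontinuation and grade 3 or higher tables are all built on this definition. For patient counts, SAP 9.1.2 adds: "At each level of patient summarization, a patient is counted once if the patient reported one or more events".

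SAP 4 lays out the columns. Patients on 2 mg in APD334-005 are shown by APD334-003 treatment (placebo, 1 mg, 2 mg, 1 mg and 2 mg combined) and then pooled. Patients on placebo in APD334-005 have one column. SAP 12 explains that this column comes from Amendment 02: responders on active treatment could be randomized to placebo, and placebo responders stayed on placebo.

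SAP 9 also says: "Baseline for the safety analysis is defined as the last pre-enrollment measurement (i.e. APD334-005 Day 1 pre-dose").

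**The concern.** Condition 2 shows that the authors had the usual idea in mind: an event that predates the first dose becomes treatment-emergent if it gets worse. Conditions 3 and 4 then let in every APD334-003 event that persists into APD334-005, whether it is stable or resolving. An APD334-003 event that worsens after the first APD334-005 dose must still be ongoing in APD334-005 or end there, so conditions 3 and 4 already catch it. Condition 2 is redundant for these events.

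Description is the whole purpose of this primary endpoint, and the tables cannot show what emerged on APD334-005 treatment. The problem is sharper where treatment changed between the studies, because an event that began on one treatment is tabulated under another.

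**Working it through.** There is no figure in the plan to reproduce: neither document gives an expected TEAE rate, a sample size or a group size. The check is of the rule, followed by an illustration.

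**Step 1. Apply the rule to each type of event**, against a rule of new onset or worsening only.

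| Event | SAP 9.1 | New or worsened only |
|---|---|---|
| Began after first APD334-005 dose | TEAE | TEAE |
| Began in 003, worsened in 005 | TEAE | TEAE |
| Began in 003, ongoing in 005, unchanged | TEAE | not TEAE |
| Began in 003, ended in 005, unchanged | TEAE | not TEAE |
| Began and ended in 003 | not TEAE | not TEAE |

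The two rules differ only on unworsened carried-over events.

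**Step 2. Compare conditions 4 and 6.** Condition 6 requires the end date to be on or after the first APD334-005 dose. Condition 4 requires only that it fall in the APD334-005 study. Consent for APD334-005 is taken before the last APD334-003 procedures (SAP 3.1), and events are monitored from consent (SAP 9.1). On one reading, an event that resolved before any APD334-005 dose would count.

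**Step 3. Follow the event into its column.**

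| 003 treatment | 005 treatment | Effect of carry-over |
|---|---|---|
| Placebo or 1 mg | 2 mg | Enters the pooled 2 mg column; prior-treatment columns show part of this |
| 2 mg | 2 mg | Same treatment; only the study period and the count are affected |
| Etrasimod (Amendment 02 responders) | Placebo | Enters the single placebo column, with no visible split by prior treatment |
| Placebo (Amendment 02 responders) | Placebo | Same treatment; only the study period and the count are affected |

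Even the prior-treatment columns do not separate new events from carried-over ones.

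**Step 4. Illustrate the size.** Both inputs are assumptions. Let p be the share of patients in a column with an event that begins or worsens in APD334-005, and q the share with at least one unworsened carried-over event. A patient with both is counted once, so the excess in patient incidence is the share with a carried-over event and no other TEAE.

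- For any dependence: between max(0, q − p) and min(q, 1 − p).
- If independent: q(1 − p).

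| | q = 10% | q = 20% | q = 30% |
|---|---|---|---|
| p = 40% | 6 points | 12 points | 18 points |
| p = 50% | 5 points | 10 points | 15 points |
| p = 60% | 4 points | 8 points | 12 points |

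Throughout this grid the bounds are 0 to q, that is 0–10, 0–20 and 0–30 points. Example: p = 50%, q = 20% gives 0.20 × 0.50 = 10 points, so 50% is reported as 60%. Per 100 such patients with one carried-over event each, the number of TEAEs rises by 20, and the number of patients with any TEAE by 10 if independent (0 to 20 otherwise).

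**Step 5. Direction.** With the same p in both columns and independence, the distortion of 2 mg minus placebo is (q in 2 mg − q in placebo) × (1 − p). At p = 50%, q of 10% and 30% gives −0.20 × 0.50 = −10 points; 30% and 10% gives +10; equal q gives 0. The sign depends on inputs that the documents do not give.

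**The case against.** The strongest defence is that this is a deliberate, inclusive rule. The objective is long-term safety, the SAP also summarises exposure from the first APD334-003 dose, and the rule hides no event. Every TEAE is listed, listings show the treatment in both studies, and most 2 mg columns are split by prior treatment. Protocol 8.2.1 and 9.8.1 also plan to tabulate onset relative to dose. This stands as a reason to keep the events in view. It does not answer the point, because no readable SAP table separates new from carried-over events, and the SAP's table list does not repeat the onset tabulation.

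A reader might infer that the rule breaks the SAP's own safety baseline. The documents do not support that. The Day 1 pre-dose baseline in SAP 9 is worded for measurements and does not mention adverse events; it helps only by analogy. SAP 9.2 and 9.3 in any case report change from both studies' baselines.

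A reader might also infer that the rule contradicts the protocol. Protocol 9.8.1 ties the term to the first dose without saying in which study, and protocol 6.11.1 uses a reporting rule. The wording is ambiguous, not clearly contradicted. SAP 12 does not visibly record the definition, but parts of that section are redacted.

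The objection to simply deleting conditions 3 and 4 is sound. Protocol 6.11.3 has severity recorded at onset and at its maximum, with no dated change visible, so worsening may not be datable. Protocol 6.11.1 counts worsening in frequency and new signs or symptoms, while condition 2 covers severity only. Deletion could lose such events, and would take carried-over serious or treatment-stopping events out of the main tables.

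**Conclusion.** The point holds as a matter of definition and presentation. Conditions 3 and 4 put unworsened APD334-003 events into every primary-endpoint TEAE table, some of them under a treatment other than the one on which they began, and the tables give no way to tell them apart. The rule cannot lower a column's TEAE count. It need not raise patient incidence, because a patient who has another TEAE is counted once.

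It is tempting to conclude that the rule makes etrasimod look worse, or placebo look worse. Neither follows: both columns can be inflated, and the net direction is unknown. The figures above rest wholly on assumed p and q, mostly with independence, and their bounds begin at zero. No formal comparison is planned, so what is affected is the reading of a descriptive endpoint and not a test. The change is worth making because it is cheap.

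**What to change.** Add a derivation flag and present each TEAE table (overall, SOC/PT, serious, relationship, severity, grade 3 or higher, discontinuation) in two parts plus the combined total:

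- **(a) Headline count:** events that began on or after the first APD334-005 dose, or that from then on worsened in severity or frequency or gained new signs or symptoms.
- **(b) Separate row or table:** APD334-003 events carried over without recorded worsening, by APD334-003 and APD334-005 treatment. Keep serious events, and those leading to discontinuation of APD334-005 medication, visible here, so that SAP 9.1.6 counts reconcile with disposition in SAP 5.1.

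Put events whose worsening cannot be dated in (b), labelled as timing unknown, and show the headline count with and without them. In condition 4, require the end date to be on or after the first APD334-005 dose. Footnote the severity table to say that a carried-over event's maximum grade may predate APD334-005. Record the definition in SAP 12. Conditions 5 and 6 are outside this point and can stay as they are.

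The cost is SAP wording and a little more programming. The headline TEAE count will be lower, and the timing-unknown group may be sizeable if dated changes in severity were not collected; the with-and-without count shows how much that matters.
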